### 6.3.2 Response Criteria

Response and progression will be evaluated in this study using the revised International Working Group criteria proposed by Cheson *et al.* (Revised Response Criteria for Malignant Lymphoma).[23] The irradiated index lesion is not included in this determination; however, tumor response of this lesion will be assessed and tabulated separately using criteria from Cheson *et al.*[23]

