#### 1.1 *Background and Relevant Literature*

Immunotherapies have emerged as a very promising option for patients with relapsed/refractory (r/r) Hodgkin lymphoma (HL) who have progressed despite second line chemotherapy, stem cell transplants and/or surface-receptor targeted agents such as brentuximab. Activity of PD-1 inhibitors in r/r HL has been documented,[2, 3] resulting in FDA approval of nivolumab for this population in May 2016. Nivolumab utilizes the patient's own immune system to eliminate cancer cells. Despite promising activity, many patients fail to achieve complete remission (CR) and/or still ultimately progress on immune modulators, and T-cell exhaustion is thought to be an important mechanism for immunotherapy failure. As in solid malignancies, it has been postulated that antigen presentation by radiotherapy (RT) is a potential tool to overcome this resistance. There are currently numerous trials using the combination of checkpoint blockade with high-dose RT (e.g. SBRT) in solid malignancies – i.e. the radiation vaccine or "RadVax" concept – yet lymphomas have not been formally studied with this approach. Lymphomas are unique in that very low-dose (2-4 Gy x 2) radiation can result in impressive response rates (30-80%), and this logically-convenient regimen is increasingly popular in an environment of otherwise declining RT use in the management of lymphomas. Traditionally, lymphomas have been considered highly immune-sensitive cancers and have served as a model for development of immune based biological therapies over the past few decades. We plan to study the combination of low dose radiation with nivolumab in patients with relapsed/refractory Hodgkin lymphoma.

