### **8.5 Secondary Endpoints**

1. The nivolumab induction CR rate is defined as the proportion of patients who achieve CR after nivolumab induction, at the week 8 evaluation.
2. The post-RT + continued nivolumab CR rate is defined as the proportion of patients who achieve CR after RT + continued nivolumab, at the week 16 evaluation (8-12 weeks post-RT). All patients who had <CR are eligible to receive RT. The denominator will include all eligible patients, regardless of whether 2 fractions of RT were administered.
3. Time to best response is defined from date of study entry to date of best response. For progressive disease patients, time to best response will be defined from study entry to date taken off study due to PD. It is assumed that most patients who are scored PD at 8-12 weeks, will continue nivolumab for another 8 weeks.
4. Duration of best response is defined from date of best response to date of disease progression, death due to any cause of last patient contact alive and progression-free.
5. Progression free survival is defined from date of study entry to date of disease progression, death due to any cause of last patient contact alive and progression-free.
6. Overall survival is defined from date of study entry to date of death due to any cause of last patient contact alive.

CONFIDENTIAL

7. Disease-free survival is defined from date of CR to date of disease progression, death due to any cause of last patient contact alive and disease-free. DFS is only computed for CR patients.
8. Toxicities will be graded and tabled separately by induction or post-RT.

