#### **8.8 Plans for Data Analysis**

1. Baseline and demographic characteristics will be summarized by standard descriptive statistics (including mean and standard deviation for continuous variables such as age and frequency and percentage for categorical variables such as gender).
2. The overall CR rate and 95% exact confidence interval will be calculated. Following an intent to treat analysis, all patients who received at least 1 dose of nivolumab are included in the analysis of the primary endpoint. Based on an exact binomial test, the number of patients with CR will determine whether the null hypothesis will be rejected (see Sample Size/Power below).
3. The nivolumab induction CR rate and post-RT + continued nivolumab CR rate and 95% confidence intervals will also be calculated.
4. Time to best response and duration of best response will be calculated and summarized separately for CR, PR, SD and PD patients.
5. Progression free survival, overall survival and disease-free survival will be estimated by the Kaplan-Meier method. Disease free survival will be computed by landmark analysis for two distinct groups: 1) DFS from week 8, for patients who achieved induction CR and 2) DFS from week 16, for patients who achieved CR after RT + nivolumab.
6. All subjects entered into the study will have detailed information collected on adverse events for the overall study safety analysis. Toxicities will be graded and tabled separately by induction nivolumab, post-induction nivolumab or post-induction RT + continued nivolumab.

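### As Section 6.3.2 is worded, progression confined to the irradiated lesion is not an event for PFS, DFS or duration of response, and more general text in the same section says otherwise

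*Combined protocol and SAP*

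**What the plan says.** Section 6.3.2 begins: "Response and progression will be evaluated in this study using the revised International Working Group criteria". After the citation it continues: "The irradiated index lesion is not included in this determination; however, tumor response of this lesion will be assessed and tabulated separately". What is kept for that lesion is thus its response, reported apart. Both copies of the text in the combined file read this way. Section 7.4 refers efficacy back to the response criteria in Section 6.3.

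Section 8.5 then builds three secondary endpoints on progression. Item 5 reads "Progression free survival is defined from date of study entry to date of disease progression" and item 7 reads "Disease-free survival is defined from date of CR to date of disease progression". Item 4 ends duration of best response at the same event. Death and last contact are the only other endpoints of follow-up. Section 8 neither gives its own definition of progression nor mentions the irradiated lesion.

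Section 8.8 item 5 adds: "Disease free survival will be computed by landmark analysis for two distinct groups". These are patients in CR after induction, followed from week 8, and patients in CR after RT plus nivolumab, followed from week 16.

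**The concern.** The exclusion refers back to a sentence about response and progression, so it reaches both. A patient whose only failure is regrowth of the irradiated node would stay progression-free, and if in CR would stay disease-free, until something happened elsewhere. Yet Sections 3.2.2 and 8.5 present these endpoints under their ordinary names, with PFS stated for the whole study population. A reader would take them as all-site endpoints that include local failure of the RT component, and might set them beside the 6-month PFS of 76.9% cited in Section 1.2 for nivolumab alone.

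The two DFS groups are also defined unequally. Induction-CR patients have no irradiated lesion, so every site counts. Post-RT-CR patients have one exempt site of known disease.

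**Working it through.** **The plan's own figure.** The only design figure is for the primary test in Section 8.9. With n = 25 and rejection at 6 or more CRs, the exact binomial gives P(X ≥ 6 | p = 0.10) = 0.0334 and P(X ≥ 6 | p = 0.30) = 0.8065. These reproduce the stated 3% and 81%. A cut-off of 5 would give a type I error of 0.098, so 6 is right. The documents state no power, event count or expected curve for PFS, DFS or duration, and the present point does not depend on the primary test.

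**The texts side by side.**

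- *Specific:* 6.3.2 names the irradiated lesion and leaves it out of the response and progression determination.
- *General, pointing the other way:* 6.3.2.3.1 takes measurable lesions (up to six) as target lesions at baseline, before any is irradiated. 6.3.2.4 requires every identified site to be followed. Table 2 counts growth of previously involved sites as PD. 6.3.2.4.2 combines target lesions, non-target lesions and new disease. None of these mentions the irradiated lesion.

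A specific exclusion normally governs general text, so the natural reading is that in-field-only progression is not an event. A reader who applied Table 2 directly would count it.

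**Direction.** For an irradiated patient let T_in be time to progression at the irradiated site, T_out time to progression elsewhere, and T_d time to death.

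- All sites: T_all = min(T_in, T_out, T_d)
- Irradiated site excluded: T_excl = min(T_out, T_d) ≥ T_all

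No patient's time can become shorter. A simulation of 200,000 patients at each of three in-field shares agreed: none had a shorter PFS under the exclusion.

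**Numbers exposed.** Section 4.5 expects about 10% induction CR, so about 25 × 0.90 = 22.5 patients would be irradiated and about 2.5 would not. With 25 patients and no censoring, each omitted event raises the PFS curve by 1/25 = 4 points until that patient has a later event.

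**Illustration of size.** Assumptions: true all-sites 6-month PFS is 76.9% in irradiated and non-irradiated patients alike; hazards are constant and proportional; a share f of the event hazard in irradiated patients arises at the irradiated site, from the start; 90% are irradiated. Then, in irradiated patients, S_excl = 0.769^(1 − f), and the reported whole-population PFS is 0.9 × S_excl + 0.1 × 0.769.

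| f (assumed) | S_excl, irradiated | Whole population | Overstatement |
|---|---|---|---|
| 10% | 78.9% | 78.7% | 1.8 points |
| 20% | 81.1% | 80.6% | 3.7 points |
| 30% | 83.2% | 82.6% | 5.7 points |
| 50% | 87.7% | 86.6% | 9.7 points |

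These lie on the high side. RT starts only after the week 8-12 assessment, with up to 3 weeks allowed for planning (Section 4.4), so early PFS time carries no post-RT in-field risk.

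**The case against.** The strongest reply is that the exclusion is deliberate and suits the design. Eligibility requires a measurable site outside the RT fields (4.1), and treatment volumes must spare a measurable lesion (5.2.3). Response of the irradiated lesion is still assessed and tabulated, so local outcome is not hidden. This justifies an out-of-field measure. It does not justify reporting that measure as PFS, DFS and duration without the label.

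It can also be said that the general text already requires all sites to count. That stands as evidence of a conflict, so a reader who infers that the exclusion is settled beyond dispute goes too far. It does not remove the problem, because only 6.3.2 speaks of this lesion.

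Three further limits stand. The endpoints are unpowered secondary estimates. Section 8.8 plans no test between the DFS groups, one of which may hold two or three patients, and no formal comparison with the cited nivolumab PFS. Deaths, new lesions and symptomatic deterioration (6.3.2.4.2) still count, so some local failures would be caught later.

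A reader might infer a larger bias by assuming that 10-30% of irradiated patients progress only in-field: 0.9 × 10-30% = 9-27 points. The documents do not support this. The rate appears nowhere in them. At six months the top end exceeds the total failure implied by the cited PFS, 100 − 76.9 = 23.1 points. The product also assumes that none of these patients has another event by then. Nor can the 30-80% response to low-dose RT in Section 1.1 be turned into 4-16 local failures (22.5 × 20% to 22.5 × 70%). Non-response includes stable disease, and the figure is for lymphomas in general.

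**Conclusion.** The point holds on the text. By the only lesion-specific rule, progression confined to the irradiated site is not an event for PFS, DFS or duration of response, and this conflicts with general text in the same section. The upward direction is certain for PFS. For DFS and duration it is certain only for a fixed set of responders, because the same exclusion also affects who is scored CR and so who enters those curves. The induction-CR DFS curve is unaffected.

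The size is unknown. About 2-10 points at six months is an illustration that rests on the assumed 10-50% in-field share, the borrowed 76.9% and 90% irradiated, and it is on the high side. A reader might infer that the primary result is compromised. This point does not show that: the primary test concerns CR counts, not progression. It should be fixed before analysis, but the trial's main conclusion does not hang on it.

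**What to change.** 1. In 8.5 items 4, 5 and 7, state that progression at any site, including the irradiated lesion, is an event.
2. In 6.3.2, state that leaving out the irradiated lesion does not apply to progression for these three endpoints, and reconcile the sentence with 6.3.2.3.1, 6.3.2.4, Table 2 and 6.3.2.4.2.
3. Report out-of-field PFS as an additional curve, labelled as such.

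The change should be confined to progression. Restricting the 6.3.2 exclusion to a separate response tabulation would bring the irradiated lesion into the primary CR count, which is a different decision. As worded here, the counting of CRs, the 25 patients and the 6-of-25 rule stay as they are.

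The cost is a few sentences and slightly less favourable PFS, DFS and duration. No new scans are needed, since the lesion is already imaged and assessed.

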#### **6.3.2.2 Guidelines for Evaluation of Measurable Disease**

**Measurement Methods:** The same method of assessment and the same technique should be used to characterize each identified and reported lesion at baseline and during follow-up. For patients having only lesions measuring at least 1 cm to less than 2 cm must use spiral CT imaging for both pre- and post-treatment tumor assessments. Imaging-based evaluation is preferred to evaluation by clinical examination when both methods have been used at the same evaluation to assess the antitumor effect of a treatment.

#### **6.3.2.3 Measurement of Effect**

##### **6.3.2.3.1 Target Lesions**

All measurable lesions up to a maximum of 6 lesions representative of all involved organs should be identified as target lesions and recorded and measured at baseline. If the protocol specified studies are performed, and there are fewer than 6 lesions identified (as there often will be), there is no reason to perform additional studies beyond those specified in the protocol to discover new lesions. For any one organ, no more than 2 lesions need to be measured. Target lesions should be selected on the basis of their size (lesions with the longest diameter) and their suitability for accurate repetitive measurements (either by imaging techniques or clinically).

##### **6.3.2.3.2 Non-Target Lesions**

All other lesions (or sites of disease) should be identified as non-target lesions and should also be recorded at baseline.

##### **6.3.2.4 Response Criteria**

All identified sites of disease must be followed on re-evaluation. Specifically, a change in objective status to either a PR or CR cannot be done without rechecking all identified sites (i.e., target and non-target lesions) of pre-existing disease.

### 6.3.2.4.2 Overall Objective Status

The overall objective response status for an evaluation is determined by combining the patient's status on target lesions, non-target lesions, and new disease.

**Symptomatic Deterioration:** Patients with global deterioration of health status requiring discontinuation of treatment without objective evidence of disease progression at that time, and not either related to study treatment or other medical conditions, should be reported as PD due to "symptomatic deterioration." Every effort should be made to document the objective progression even after discontinuation of treatment due to symptomatic deterioration that may include weight loss >10% of body weight, worsening of tumor-related symptoms, and/or decline in performance status of >1 level on ECOG scale.

### 6.3.3 End of Study Visit

At the end of study visit – the second response assessment, 8-12 weeks after the first response assessment – FDG-PET will be performed, the patient will be evaluated for toxicities, and a final blood draw will be taken for correlative biomarkers. Patient charts will be reviewed for progression, response, and overall survival.

### 6.4 Unscheduled Visits

Unscheduled visits may occur per patient request. If an unscheduled visit occurs within 1 week of the next scheduled visit, the unscheduled visit will substitute for the next scheduled visit, and that next scheduled visit will be canceled.

### 6.5 Subject Withdrawal

Subjects may withdraw consent at any time for any reason or be dropped from the trial at the discretion of the investigator should any untoward event occur. In addition, a subject may be withdrawn by the investigator or the Sponsor if enrollment into the trial is inappropriate, the trial plan is violated, or for administrative and/or other safety reasons. Specific details regarding discontinuation or withdrawal are provided in Section 7.1.4 – Other Procedures. A subject must be discontinued from the trial for any of the following reasons:

- The subject or legal representative (such as a parent or legal guardian) withdraws consent.
- Unacceptable adverse experiences as described in Section 5.2.1.2
- Intercurrent illness that prevents further administration of treatment

CONFIDENTIAL

- Investigator's decision to withdraw the subject
- The subject has a confirmed positive serum pregnancy test
- Noncompliance with trial treatment or procedure requirements
- The subject is lost to follow-up
- Administrative reasons

The End of Treatment and Follow-up visit procedures are listed in Section 6 (Protocol Flow Chart) and Section 7.1.5 (Visit Requirements). After the end of treatment, each subject will be followed for 30 days for adverse event monitoring (serious adverse events will be collected for 90 days after the end of treatment as described in Section 7.2.3.1). Subjects who discontinue for reasons other than progressive disease will have post-treatment follow-up for disease status until disease progression, initiating a non-study cancer treatment, withdrawing consent or becoming lost to follow-up. After documented disease progression each subject will be followed by telephone for overall survival until death, withdrawal of consent, or the end of the study, whichever occurs first.

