#### **1.4 Dose Rationale**

Nivolumab has been studied in r/r HL patients at a dose of 3 mg/kg, infused over 60 minutes, administered every 2 weeks.[2, 3] This had been a standard dose regimen for nivolumab across disease sites and was the manufacturer- and FDA-recommended dose regimen for r/r HL. (However, the FDA recently approved an every-4-week regimen of nivolumab, 480 mg infused over 30 minutes.) Treating physicians will have the discretion of treating every 2 weeks or every 4 weeks. Among patients tested for efficacy, grade 3 or higher toxicities included: thrombocytopenia in 33%, increased lipase in 12%, lymphopenia in 7%, neutropenia in 6%, and pneumonia in 5%. [11] Any grade toxicities included upper respiratory tract infection in 48%, fatigue in 43%, neutropenia in 37%, fever in 35%, cough in 35%, thrombocytopenia in 33%, lymphopenia in 32%, increased AST in 32%, and rash in 31%, among other toxicities. [11] For patients who subsequently undergo allogeneic hematopoietic stem cell transplantation, toxicity data are unclear, however there is a concern for increased severe acute graft versus host disease. [11]

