### **3.2.2 Secondary Study Endpoints**

- Nivolumab induction CR rate.
- Post-RT + nivolumab CR rate.
- Progression-free survival (PFS) for entire study population.
- Overall survival (OS) for the entire study population.
- Disease free survival (DFS) for the nivolumab induction CR cohort and for the RT + continued nivolumab CR cohort.
- Duration of immunotherapy use for the entire study population, nivolumab only cohort, and nivolumab + RT cohort.
- Time to best response.
  - Duration of response, Biosamples (blood and, where available, tumor) obtained from patients before and at serial time points during treatment will be analyzed. The primary goals for the basic studies with these human samples will be high dimensional (15-17 color) flow cytometry to analyze T cell subsets (including naïve, effector, memory (effector memory and central memory), effector memory RA, exhausted, Th1, Treg and Tfh), co-expression of sets of multiple inhibitory receptors by relevant T cell subsets, transcription factor expression, and T comprehensive functional analysis (expression of cytokines, chemokines, cytotoxic molecules, and degranulation). These studies will focus on sophisticated immune phenotyping and defining correlates of response.
  - In addition, the following markers will be studied: CD3, CD4, CD8, CD25, CD39, CD73, CD127, FOXP3, CD122, CD212 (IL-12R), HLA-DR, CD14, CD19, CD56, CD69, FAS-L, Granzyme B, IL-2, IL-4, IL-10, IL-12, Rantes, IFN- $\gamma$ , TGF- $\beta$ , GM-CSF, sIL-2R.
- Change from baseline in tumor FDG uptake on PET/CT after initiation of nivolumab.
- Association between change in tumor FDG uptake and progression-free and overall survival.
- Based on change in tumor FDG uptake after initiation of nivolumab, determine which patients have FDG "flare."
- Association between FDG flare and response, progression-free survival, overall survival, and biomarker changes.
- Exploratory analyses will be conducted in changes in markers between induction nivolumab responders (CR) and non-responders (<CR), between post-RT responders (CR/PR vs. <PR), and between RT and no-RT cohorts.

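### Section 6.5 plans no survival follow-up for a patient who starts another cancer therapy without documented progression, although OS is an endpoint for the entire population

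*Combined protocol and SAP*

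**What the plan says.** Section 6.5 (the wording is the same in both copies of the protocol in the file) sets up two follow-up streams after study treatment.

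- Disease status: "Subjects who discontinue for reasons other than progressive disease will have post-treatment follow-up for disease status until disease progression, initiating a non-study cancer treatment". Withdrawal of consent and loss to follow-up also end this stream.
- Survival: "After documented disease progression each subject will be followed by telephone for overall survival until death". Withdrawn consent and the close of the study also end this stream.

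The endpoints are wider than these streams. Section 3.2.2 lists "Progression-free survival (PFS) for entire study population" and "Overall survival (OS) for the entire study population". Section 8.5, item 6 reads: "Overall survival is defined from date of study entry to date of death due to any cause of last patient contact alive" (the second "of" evidently stands for or). Items 5 and 7 of 8.5 define PFS and DFS to progression or death, with censoring at last contact, and do not mention new therapy. Section 8.8 estimates all three by Kaplan-Meier. Item 3 of the Exploratory Analyses uses PFS and OS again as outcomes for the FDG flare, by log-rank test and Cox regression.

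**The concern.** A patient whose disease has not progressed and who begins a different cancer therapy leaves the first stream at that moment and has not met the trigger for the second. Nothing in 6.5 starts survival contact at that point. The situation is realistic on the protocol's own terms, because section 3.1 lets nivolumab stop for intolerance or by the oncologist's decision as well as for progression.

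At stake is the OS estimate. Under 8.5 such a patient is censored at the last contact alive, which would fall near the change of treatment. Kaplan-Meier treats censoring as unrelated to later risk of death. A decision to change therapy may well be related to that risk, so the assumption is doubtful for exactly these patients. With 25 patients, each one carries 1/25 = 4 percentage points of the cohort.

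**Working it through.** **Primary design figures, as a check that they are not involved.** Inputs from section 8.9: n = 25, reject at 6 or more CRs, 10% against 30%, one-sided exact test.

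- Actual alpha = P(X ≥ 6 | n = 25, p = 0.10) = 0.0334; the plan states 3%.
- Power = P(X ≥ 6 | n = 25, p = 0.30) = 0.8065; the plan states 81%.

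Both reproduce. The endpoint is CR at the response assessments, so survival follow-up changes neither figure.

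**Who is followed under 6.5.**

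| Patient stops study treatment | Disease-status stream | Survival calls |
|---|---|---|
| With documented progression | Does not apply | Start |
| Without progression, no other therapy | Continues | Start once progression is documented |
| Without progression, other therapy begins | Ends | Not started, unless progression is later documented by some other route |

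The third row is the gap.

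**Whether another section closes it.**

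- 6.3.3: charts are reviewed for survival, but this is stated under a visit 8-12 weeks after the first response assessment, with no later schedule or cut-off.
- 3.1.3: care off study follows the treating physician's judgement; no data collection is stated.
- 6.5.1: the public survival look-up is for patients who withdraw consent.
- 6.5: serious adverse events, which include fatal ones, are collected for 90 days after treatment ends.
- 9.2 and the Reporting Process text in 9.4.1: possibly related later serious events, and deaths once known, must be reported. Neither rule obliges anyone to find out.
- 6.5 also points to sections 7.1.4, 7.1.5 and 7.2.3.1. Section 7 runs from 7.1 to 7.5 without such subsections, so no rule is found there.

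**Size, under assumption.** The documents give no switch rate. Let k of the 25 patients switch before a fixed time t and have unknown vital status at t, and let a of the other 25 − k be known alive. OS at t then lies between a/25 (all k dead) and (a + k)/25 (all k alive), so the width is k/25.

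- k = 2: 2/25 = 8 points
- k = 3: 3/25 = 12 points
- k = 5: 5/25 = 20 points
- k = 6: 6/25 = 24 points

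**Direction.** Suppose OS at t is 90% in non-switchers and switchers are censored at the switch, so that Kaplan-Meier reads about 90%. All survival values here are assumed.

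- k = 2, switchers' OS 70%: true OS = (23 × 0.90 + 2 × 0.70)/25 = 88.4%; the estimate is 1.6 points too high.
- k = 2, switchers' OS 97%: (23 × 0.90 + 2 × 0.97)/25 = 90.6%; 0.6 points too low.
- k = 5, switchers' OS 70%: (20 × 0.90 + 5 × 0.70)/25 = 86.0%; 4.0 points too high.
- k = 5, switchers' OS 97%: (20 × 0.90 + 5 × 0.97)/25 = 91.4%; 1.4 points too low.

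The sign depends on how switchers fare, which the documents do not tell us.

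**The case against.** The strongest reply is that deaths after a switch need not be lost. The chart review in 6.3.3 makes no exception for switchers and names no end date, so a continuing review is a possible reading. The 90-day window and the reporting rules catch early, related or otherwise known deaths. The telephone rule covers each subject, so a switcher whose progression later comes to light would enter it. This stands in part: it is too strong to say that such deaths go uncollected or that a switcher can never reach survival follow-up. What remains is that no rule ensures ascertainment, most plainly for a switcher who dies without documented progression.

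A second reply is that 8.5 already censors at last contact, so 6.5 does not contradict it. That is formally so, and naming the whole population fixes the analysis set rather than the length of follow-up. But the censoring would then be created by the follow-up rule itself, at a point that may carry prognostic information.

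A third reply is that stopping disease follow-up at new therapy is a recognised choice. This stands. Telephone contact without scans could not reliably date progression by the response criteria in 6.3.2.

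A reader might also infer that the protocol foresees transplant in this cohort and would hide its harm, because section 1.4 says "there is a concern for increased severe acute graft versus host disease". The documents do not support that. The sentence is background on published toxicity data, forecasts nothing for these patients and concerns an acute complication, and a serious case judged possibly related to study treatment is reportable under 9.2.

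**Conclusion.** The gap holds for OS: under 6.5 a patient who starts another therapy without documented progression has no planned survival follow-up, and the other provisions cover this only in part. The 8 to 24 point width of the bounds rests on an assumed 2 to 6 switchers among 25, all with unknown later vital status and everyone else's status known. It describes lost information, not an expected bias.

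Two stronger readings should be avoided. One is that OS would be overstated; the illustration runs both ways. The other is a figure for DFS. Taking 30% of 25 gives 7.5 CRs, and one missed event would be 1/7.5, about 13 points. But section 8.8 estimates DFS separately for induction CRs and post-RT CRs, so the pooled figure matches no planned analysis.

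The importance is moderate. OS, PFS and DFS are secondary and have no power calculation, and the flare analyses are exploratory. The primary CR endpoint, sample size, power and alpha are untouched. The change is still worth making, because vital status is cheap to collect as the study runs and harder to recover afterwards.

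**What to change.** Amend 6.5 so that, from the end of study treatment, every treated patient is followed for survival by telephone or chart, with or without progression and whatever therapy comes next, until the patient dies, withdraws consent or the study closes. Record the start date and type of the first subsequent cancer therapy.

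For PFS and DFS, either stopping or continuing disease follow-up at new therapy is defensible. Sections 6.5 and 8.5 should be reconciled by stating which applies and how new therapy is handled in the analysis.

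The cost is a few more calls or chart checks, using the telephone contact already planned for patients with progression, plus two CRF fields. No extra scans are needed for the survival part.
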